4.7.1.3 CRT AutoAdapt (CRT only)

The hemodynamic benefit of CRT depends on the setting of an AV-delay that allows the full atrial contribution for optimal filling of the ventricles and the setting of a ventricular pacing configuration that ensures ventricular synchronization for optimal ejection. Observational studies have identified suboptimal programming of the AV and VV delays as determinant factor of a poor response to CRT²⁵. Since physiologic conditions change over the day and also on a longer scale with cardiac remodeling, the settings need frequent adaptation to ensure optimal benefit of CRT. Therefore, the adaptive CRT AutoAdapt algorithm (see Figure 5) can be used to adjust the AV-delay and set the ventricular pacing configuration to BiV or LV, based on periodic automatic measurement of electrical intra-cardiac conduction times (see Table 3). (*Ventricular pacing configuration 'LV' is sometimes called 'LV only' pacing configuration.*)

The pre-conditions for CRT AutoAdapt activation or continuation are an atrial heart rate below 100 bpm and an AV conduction time after pace of less than 250 ms. Switching to *LV only pacing* is only allowed if LV Capture Control is enabled. This is to ensure that the LV only mode cannot be activated if the LV pacing threshold is not sufficient.

If the measurements of conduction times indicate that the condition for starting/continuing CRT AutoAdapt are not fulfilled (see Figure 5), the algorithm switches back to the BiV pacing settings that the physician programmed before activating CRT AutoAdapt.

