8.1.4 Methods

During the course of the study, all clinical procedures are performed according to clinical routine. More detailed information can be found in the technical manual and in supporting study documents. The Automatic LV VectorOpt test for LV vector selection, and the AV Opt test or CRT AutoAdapt feature for AV delay optimization have to be used mandatorily in the respective devices unless contraindicated. The corresponding time schedule is described in section 9.1. All parameters and measurements that are recorded within the study are described in this section and are documented on the corresponding electronic case report forms (eCRFs). The investigator is required to use an electronic signature to approve the content of the data reported in the eCRFs. BIOTRONIK will monitor the content of the eCRFs as described in section 10. Data will be documented at the following points in time:

- Enrollment/Baseline
- Implantation
- Pre-hospital discharge
- 3-month follow-up
- 6-month follow-up
- 12-month follow-up
- Termination

The following events can be documented at any time:

- Adverse Events
- Device Deficiencies
- Premature termination

Source data, e.g. medical records, has to be available for all data entered in the eCRFs, unless specified differently by this CIP (compare sections below). Generally, the eCRF may be accepted as source document for the assessment of design, usability, acceptance and other subjective assessments by the investigator. However, the use of a site-specific source data sheet is recommended in these cases. Electronic CRFs will be verified at monitoring visits by the sponsor's representative.

Information from electronically delivered source data (e.g. via ReportShare, exported programmer files or medical records about (S)AEs) can be used for remote source data verification when pseudonymization thereof has been verified.

Patients have to consent to the use of their medical data in the patient file by signing the informed consent form.

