8.1.4.9 CRT AutoAdapt (only Acticor 7 and Rivacor 7 CRT-Ds)

At implantation and/or pre-hospital discharge CRT AutoAdapt shall mandatorily be programmed 'ON' in all CRT-D patients that are implanted with Acticor 7 or Rivacor 7, with the exception of patients with AV block, for whom this feature is contraindicated. (Note: CRT AutoAdapt is not available in Rivacor 5.) The feature may be programmed 'OFF' in exceptional cases without causing a deviation from this clinical investigator plan, provided that the investigator gives a sound reasoning for his decision, e.g. special medical condition of the patient.

At 3-month follow-up the following data will be recorded:

- Was the feature programmed 'ON'?
- If "no", why not?
- Programmed setting for ventricular pacing and programmed AV delays
- Mean percentage of CRT pacing since last follow-up
- Mean percentages of adaptive BiV pacing, programmed BiV pacing and adaptive LV pacing, respectively, since last follow-up
- Mean adapted AV delay after pace/sense
- Assessment of the feature by the investigator:
 - Programmability (Score: "Very easy/easy/adequate/difficult/very difficult")
 - Clinical acceptability of the algorithm's decisions (Score: "Very good/good/adequate/poor/very poor")
 - Overall assessment of the CRT AutoAdapt feature (Score: "Very good/good/adequate/poor/very poor")

The eCRF may be accepted as source document for the assessment of the CRT AutoAdapt feature. However, the use of a site-specific source data sheet is recommended.

- Is the programming of CRT AutoAdapt maintained at the end of the follow-up? If "no", why not?

At 3-month and subsequent follow-ups it is the investigator's decision to leave the feature activated or to deactivate it.

If the feature remained active until the 12-month follow-up, the investigator will again be asked for an overall assessment of CRT AutoAdapt.

In addition to the data collected during follow-up visits, Home Monitoring data may be analysed with regard to the behaviour of the algorithm, e.g. mean percentage of adaptive BiV pacing, programmed BiV pacing and adaptive LV pacing, respectively.

8.1.4.10 AV delay optimization (for VR-T DX, DR-T, and Rivacor 5 HF-T and HF-T QP devices)

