9.1 Overview

Table 5 : Overview of study procedures. The exact reference time for the 3-, 6- and 12-month follow-up is defined as 92 days, 183 days and 365 days after implantation, respectively. The applicable time window is \pm 30 days around this reference time.

Investigations	Enroll- ment	Implan- tation	PHD	3- Month FU	6- Month FU	12- Month FU
Verification of in- and exclusion criteria	x					
Patient informed consent	x					
Documentation of demographic and health status data	x					
Documentation of cardiovascular medication	x	x	x	x	x	x
Documentation of indication for ICD/CRT-D therapy (incl. available diagnostics)	x					
ICD/CRT-D implantation		x				
Assessment of ICD/CRT-D shape		x				
Assessment of Plexa S DX Lead handling		x				
Assessment of Selectra catheter handling		x				
Record device based sensing, pacing threshold and impedance values		x	x	x	x	x
Evaluation of system performance		x	x	x	x	x
Evaluation of tachyarrhythmia episodes		x	x	x	x	x
Registration at HM Service Center, hand out CardioMessenger		(x)	x			
Home Monitoring 'ON'		x	x	x	x	(x)
Recording Episode IEGMs (event triggered): 'ON'		x	x	x	x	(x)
Automatic LV VectorOpt test		(x)	x	(x)		
CRT AutoAdapt 'ON' (Acticor/Rivacor 7 CRT-D)		(x)	x	(x)	(x)	(x)

Investigations	Enroll- ment	Implan- tation	PHD	3- Month FU	6- Month FU	12- Month FU
Evaluation of CRT Auto Adapt Feature (Acticor/ Rivacor 7 CRT-D)				x		(x) ⁴
AV Opt Test (VR-T DX/ DR-T/Rivacor 5 CRT-D)			x	(x)		
Documentation of Quick Check				x	x	x
Documentation of MPP settings (for HF-T QP)		x	x	x	x	x
Documentation of MRI examination			x	x	x	x
Assessment of patient's wearing comfort (in case of exchange)				x		
Evaluation of ATP statistics page						x
eCRF completion	x	x	x	x	x	x
Provision of programmer data via ReportShare		x	x	x	x	x
Adverse event and device deficiency reporting	x	x	x	x	x	x
Regular study termination						x

x=if applicable, (x)=optional

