9.3 Implantation

The implantation can only be performed after enrollment of the patient. The implantation procedure will follow the clinical routine, and the instructions for use for the investigational product have to be adhered to. Please refer to section 8.1.4.3 for further details.

All patients will be implanted with one of the Acticor 7 or Rivacor 7/5 devices and patients with VR-T DX devices will additionally be implanted with a Plexa S DX with DF4 connector (65/15, 65/17).

Patients with planned upgrade from pacemaker or ICD to ICD or CRT-D or device exchange may also be included in the study.

1. Perform lead measurements via pacing sensing analyzer (any analyzer can be used but BIOTRONIK device recommended; no documentation in eCRF required)
2. Perform device-based measurements of pacing thresholds and sensing amplitudes, pacing impedances and shock impedances via Renamic programmer (see 8.1.4.15)
3. Evaluate system performance (sensing and pacing)
4. Document and evaluate tachyarrhythmia episodes, if applicable (e.g. if defibrillation threshold test was performed) (see 8.1.4.16)
5. Optional at implantation: Perform Automatic LV VectorOpt Test (see 8.1.4.8)
6. Program the following mandatory device settings:
 - Home Monitoring 'ON'
 - For CRT-D patients implanted with Acticor 7 or Rivacor 7 devices (with exception of patients with chronic complete AV block), optional at implantation: CRT AutoAdapt 'ON'
 - Recording episode IEGMs (event-triggered) 'ON'
7. Document current medication on the medication log (see 8.1.4.21)
8. For HF-T QP patients: Document MPP settings, if applicable (see 8.1.4.12)
9. Assess the ICD/CRT-D design (see 8.1.4.5)
10. Assess the of Plexa S DX lead handling, if applicable (see 8.1.4.6)
11. Assess the Selectra catheter handling, if applicable (see 8.1.4.7)
12. Register to Home Monitoring Service Center (optional at implantation)
13. Complete the electronic Case Report Form (eCRF) in a timely manner
14. Provide programmer data (see 8.1.4.19)
15. Report all adverse events. In case of a serious adverse event, or adverse device effect (ADE), please provide the information immediately to BIOTRONIK, and inform the ethical committee, if required. Report adverse events within the indicated timelines (see section 18.9).

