9.4 Pre-hospital discharge

Prior to discharge from the hospital (at least 4 hours after the implantation procedure but not later than 10 days afterwards) the implanted system has to be checked again. All data obtained during the pre-hospital discharge follow-up visit (PHD) have to be recorded on the respective eCRF.

The following procedures are required.

1. Reprogram ICD settings as applicable to optimize ICD/CRT-D function
2. Perform device-based measurements of pacing thresholds and sensing amplitudes, pacing impedances and shock impedances via Renamic programmer (see 8.1.4.15)
3. Evaluate system performance (sensing and pacing)
4. Document and evaluate tachyarrythmia episodes, if applicable (see 8.1.4.16)
5. Perform Automatic LV VectorOpt Test (if not yet done at implantation) for all CRT-D patients (mandatory, see 8.1.4.8)
6. Perform AV Opt Test for all patients with VR-T DX or DR-T devices and for patients with Rivacor 5 triple-chamber devices (see 8.1.4.10)
7. Program the following mandatory device settings:
 - Home Monitoring: 'ON'
 - For CRT-D patients implanted with Acticor 7 or Rivacor 7 devices (with exception of patients with chronic complete AV block): CRT AutoAdapt 'ON'
 - Recording episode IEGMs (event-triggered): 'ON'
8. Program the following recommended device settings:
 - For patients implanted with Acticor 7 or Rivacor 7 devices: QuickCheck 'ON'
 - For patients implanted with VR-T DX devices: activate alert for 'detection of atrial monitoring episode' in HMSC
9. Document current medication on the medication log (see 8.1.4.21)
10. For HF-T QP patients: Document MPP settings, if applicable (see 8.1.4.12)
11. Document MRI examinations since implantation, if applicable (see 8.1.4.14)
12. Register to Home Monitoring Service Center and hand over the CardioMessenger, if not yet done

The patient should be familiar with the transmission function and right placing of the CardioMessenger and has to be trained accordingly before leaving the hospital.

In the time between the follow-up visits it is recommended to check the Home Monitoring transmission on a regular basis. If data transmission is missing, the investigator or study nurse has to contact the patient to clarify the reason for non-transmission.
13. Complete the electronic Case Report Form (eCRF) in a timely manner
14. Provide programmer data (see 8.1.4.19)

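### The protocol gives two different AV-block exemptions from mandatory CRT AutoAdapt, and the SAP reason code for switching it off follows only the narrower one

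*Protocol*

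**What the plan says.** Protocol 8.1.4.9 makes CRT AutoAdapt mandatory ON, at implantation and/or pre-hospital discharge, in CRT-D patients with an Acticor 7 or Rivacor 7, "with the exception of patients with AV block, for whom this feature is contraindicated". SAP 7.5 and SAP 9.2.7 reproduce this text as excerpts. The same protocol section adds a release: "The feature may be programmed 'OFF' in exceptional cases without causing a deviation", provided the investigator gives sound reasons.

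Protocol 9.4, step 7, opens with "Program the following mandatory device settings" and includes the same devices "with exception of patients with chronic complete AV block): CRT AutoAdapt 'ON". Protocol 9.3 carries the same narrower exemption, "with exception of patients with chronic complete AV block), optional at implantation: CRT AutoAdapt 'ON", so there the setting is not compulsory. Table 5 in Protocol 9.1, in the row "CRT AutoAdapt 'ON' (Acticor/Rivacor 7 CRT-D", likewise marks it optional at implantation and not optional at discharge.

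Protocol 8.1.4 says generally that the optimization features "have to be used mandatorily in the respective devices unless contraindicated".

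For secondary endpoint 3, item g (reasons for deactivation at 3 months), SAP 14.2 defines the variable COAUAOFF with two options: chronic complete AV block, marked as the contraindication, and *Other*.

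**The concern.** A site applying 8.1.4.9 and a site applying 9.4 reach different conclusions for the same patient. Under 8.1.4.9, a patient with lesser or non-chronic AV block is exempt because the feature is contraindicated. Under 9.4 that patient must have it switched on, and can be OFF only through the exceptional-case clause with a justification.

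Two things are at stake. The first is consistency of a safety-related programming instruction. Protocol 6.2.3 counts the risks of CRT AutoAdapt as study-specific precisely because the study makes activation mandatory, so the scope of the mandate decides who bears that risk. The same section names AV block as a situation in which the repeated conduction measurements could produce long AV times. It also describes a mitigation, so no unmitigated harm is claimed here.

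The second is the meaning of endpoint 3, item g. The reported frequency of contraindication would not match the definition of contraindication in the section that defines the procedure.

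**Working it through.** No sample size, power or error rate is involved, so the check sets side by side every place where the documents limit the feature by AV conduction.

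| Place | Scope of the restriction | Status |
|---|---|---|
| Protocol 8.1.4.9; excerpts in SAP 7.5 and 9.2.7 | AV block, no degree or chronicity | Exempt, called contraindicated |
| Protocol 9.4 | Chronic complete AV block | Exempt from a mandatory setting |
| Protocol 9.3 | Chronic complete AV block | Exempt from an optional setting |
| SAP 14.2, item g code | Chronic complete AV block | Called contraindication |
| Protocol 4.7.1.3 | Chronic third-degree AV block | Generally not indicated |
| Protocol 6.2.3 | Chronic AV block, no degree | Generally not indicated |
| Protocol 4.7.1.3, pre-condition | "an AV conduction time after pace of less than 250 ms" | Condition for the algorithm to run |

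**Step 1: apply 8.1.4.9 and 9.4 to each type of patient.**
- No AV block: mandatory ON under both. They agree.
- Chronic complete AV block: exempt under both. They agree.
- First-degree, second-degree or non-chronic AV block: exempt as contraindicated under 8.1.4.9, mandatory ON under 9.4. They conflict.

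**Step 2: look for a text that settles the third case.**
- The proviso in Protocol 8.1.4 sends the reader back to whatever is contraindicated. The places that name the contraindication are 8.1.4.9 with its SAP excerpts (broad) and the SAP 14.2 code (narrow), so the proviso inherits the conflict.
- The statements in 4.7.1.3 and 6.2.3 concern indication, not contraindication, and differ from each other.
- The pre-condition in 4.7.1.3 is a conduction time, not a degree of block.
- The instructions for use are not part of the documents available.

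**Step 3: follow the third case into the analysis.** If such a patient is OFF at 3 months, COAUAOFF can only be *Other*. SAP 14.2 lists the text for each *Other* case, and SAP 5.4 allows free text to clarify other data, so the case can be recovered by reading the listing. It is not in the contraindication frequency.

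**Step 4: bound the number.** Protocol 8.2.4 plans 15 HF-T and 52 HF-T QP devices among 127 patients:

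15 + 52 = 67; 67 / 127 = 0.528, or 52.8%.

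This is a ceiling, not an estimate. It includes any Rivacor 5 CRT-Ds, which lack the feature. The documents give neither the 7-series share nor the frequency of AV block, so the number under conflicting rules lies somewhere between 0 and 67.

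**The case against.** The strongest reply is that 8.1.4.9 is shorthand. Protocol 9.3, 9.4 and the SAP code all use the narrow term, 4.7.1.3 is close to it, and the SAP repetitions of the broad wording are only excerpts. Protocol 6.2.3 also foresees the algorithm lengthening its measurement interval when conduction is intermittently impaired, which suggests use outside permanent block. This may explain how the mismatch arose. It does not remove it: the section that defines the procedure still states a broader contraindication than the step list sites follow at discharge.

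A second reply is that sites are bound to the instructions for use (Protocol 4.5 and 9.3), which may be clear. That is possible and cannot be checked here, but the protocol and SAP would still need to agree with each other.

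A third is that little follows in practice. An investigator may leave the feature OFF with reasons and no deviation. The algorithm returns to the physician's programmed biventricular settings when its conditions are not met. Item g is descriptive, and its *Other* reasons are listed anyway. All of this stands, and it limits the consequence: no patient is compelled to have the feature on, and the information is not lost. What remains is that OFF is a justified exception under one section and a contraindication under another, and that the printed frequency follows only the narrower scope.

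It is also fair that the ceiling of 67 says little about likely size.

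**Conclusion.** The point holds. Protocol 8.1.4.9 and 9.4 set conflicting rules for patients with AV block that is not both chronic and complete. The SAP carries both scopes: the broad one in 7.5 and 9.2.7, the narrow one in 14.2. It should be corrected.

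The effect is confined to a programming instruction and to the reason frequencies in secondary endpoint 3, item g, where each OFF patient with lesser or non-chronic block is one count of *Other* that 8.1.4.9 would call contraindicated. The number of such patients is unknown, between 0 and 67. Endpoint 3 carries no hypothesis; the primary endpoint and the sample sizes of 114 and 127 are unaffected.

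The conclusion rests on the printed text alone and takes AV block without a qualifier to mean what it says. It takes no position on which scope is clinically right.

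**What to change.** Reconcile Protocol 8.1.4.9, 9.3, 9.4, 4.7.1.3 and 6.2.3 with SAP 7.5, SAP 9.2.7 and the SAP 14.2 reason code, so that one exemption applies throughout. The choice belongs to the sponsor's clinical experts. Then align the COAUAOFF options with it, so that every exempt patient appears as exempt in the item g frequencies rather than under *Other*.

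Optionally, tabulate exempt patients by degree of AV block using MHAVBTYP (SAP 8.2.1). That is a medical-history item recorded only when a history of AV block is reported. It gives degree I, II or III, not chronicity or status at discharge, so it describes the group but cannot define it. If the agreed wording keeps chronicity, that would have to come from the free text.

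The cost is a wording correction in the protocol, matching SAP excerpts, and one changed or added reason-code option. Any reasons already entered might need recoding from the free text. Protocol 13 treats changes that affect procedures or analysis as substantial, so ethics committee approval may be needed. No new measurements are required.

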8.1.4.11 QuickCheck

The use of QuickCheck is optional during the study. However, if QuickCheck was used, the following data should be recorded:

- Reason for activation of QuickCheck – select from the following:
 - Routine check (instead of or in addition to scheduled HM follow-ups)
 - Observation in Home Monitoring Data
 - Home Monitoring Alert
 - Patient demand (reassurance)
 - Patient demand (symptoms)
 - Other (please describe)
- QuickCheck was triggered – select from the following:
 - while patient was on the phone
 - after the patient has contacted the site
 - after the site has contacted the patient
 - without patient contact
- QuickCheck was triggered by - select from the following:
 - nurse
 - physician
 - cardiac technician
 - other (please describe)
- Was the QuickCheck transmission fast enough? [yes/no/no opinion]
- Please estimate: How often will you use QuickCheck for this patient over the course of the next year? (not at all/once/bi-annually/quarterly/monthly/more than monthly/no opinion)
- To what extent do you agree to the following statement (Score: "Strongly agree/Somewhat agree/Neither agree nor disagree/Somewhat disagree/Strongly disagree"):
 - QuickCheck is a useful tool for remote patient management.
 - QuickCheck allows informed therapy decisions.
 - I perceive QuickCheck as a reassuring feature of the ICD therapy.
 - My patient perceives QuickCheck as a reassuring feature of the ICD therapy.
- Overall assessment of the QuickCheck feature (Score: "Very good/good/adequate/poor/very poor")

The eCRF may be accepted as source document for assessment of QuickCheck. However, the use of a site-specific source data sheet is recommended.

In addition, the time needed for data transmission (from triggering to availability in HMSC) will be retrieved from the HMSC.

8.1.4.12 Usage and settings of MultiPole pacing (MPP)

The use of MultiPole Pacing (MPP) is optional within the study. However, if MPP was used in HF-T QP patients, the following data should be recorded:

Programmed vectors, pacing thresholds, programmed pacing amplitudes, LV sensing polarity, sensing amplitude, LV-LV delay and LV-RV delay.

8.1.4.13 Improved CRT response after change of LV pacing vector

At the 6- and 12-month follow-up the investigator is asked to evaluate if a previous change of the LV pacing vector improved CRT response. The formerly used and the new vectors have to be documented.

8.1.4.14 MRI examinations

If an MRI examination was performed during the course of the study (independently from the study), the following data will be recorded:

Use of MRI AutoDetect, Use of MRI Test Mode, Adverse Events/Device Deficiencies related to the MRI procedure or activation of MRI AutoDetect.

8.1.4.15 Lead measurements with Renamic programmer at implantation and each follow-up

The system performance, i.e. appropriate sensing and pacing is evaluated at the end of the implantation procedure and **at the end** of each follow-up by either manually or automatically triggered lead measurements. For this purpose the investigator performs the threshold tests, determines pacing impedance and painless shock impedance and performs P/R-wave amplitude measurements in all available channels (in DX leads also sensing measurements in the atrial channel). In the RA and RV the pulse width must be 0.4 ms, in the LV any pulse width can be chosen. For CRT-D patients measurement of LV pacing vectors with the Automatic LV VectorOpt feature is **mandatory**, either at Pre-hospital discharge or at time of the 3-month follow-up. Pacing polarities of the LV channel must be documented. The type of programmer is also documented.

If no manual measurements were performed during the on-site follow-up, the values which were automatically measured by the device the previous day are acceptable.

The investigator is asked to assess the sensing and pacing performance at the end of each follow-up (including storing of an IEGM snapshot): The sensing of the lead will be assessed as "adequate" (= the device sensed the current rhythm correctly) or "inadequate". In the ventricles the additional option "no intrinsic rhythm" (= patient is fully paced) is available to describe if an evaluation of sensing is not possible. In case the sensing is considered inadequate, the reason "oversensing", "undersensing", "not measurable" (= quality/content of IEGM does not allow any discrimination if senses are correct (e.g. lead dislodgement)) or "other" will be determined. The pacing of the lead will be assessed as "adequate" (=successful stimulation) or "inadequate". In case the pacing is considered inadequate, the reason for the evaluation is required. Possible options are "non-capture" (= no evidence of depolarization after pacing), "no output" (= failure to pace: impulses are generated by the device but is not transferred to the myocardium), "not measurable" (= quality/content of IEGM does not allow any discrimination if stimulation is successful) or "other".

At the end of the on-site follow-up procedure the full follow-up data set shall be provided to the sponsor and will be used for source data verification (see section 8.1.4.19).

